Study Protocol

A Phase II, Open-Label, Single-Arm Study to Assess the Efficacy and Safety of Decapeptyl[®] SR (3 mg and 11.25 mg formulations) when administered by subcutaneous injection.

Short Title: The DISC study

STUDY SU/2006/2424 Protocol Version Number 1.1 20 June 2008 EUDRACT NO: 2006-006595-38

Study Sponsor:

University Hospitals Bristol NHS Foundation Trust R&E Department [name] [contact]

Chief Investigator:

[name] Consultant Urologist Department of Urology Bristol Royal Infirmary [name] [contact] [contact] E-mail: [contact]

Sponsor Contact for SAE Reporting:

Research and Effectiveness Department [name] [contact] [contact]

Ipsen Emergency Contact:

[name] Local Pharmacovigilance Manager [contact] hours) [contact]

PROTOCOL SIGNATURES

Investigator Signature:

I have read and agree to the Final version of the protocol dated 20th April 2007 and entitled: 'A Phase II, Open-Label, Single-Arm Study to Assess the Efficacy and Safety of Decapeptyl[®] SR (3 mg and 11.25 mg formulations) when administered by subcutaneous injection'. I am aware of my responsibilities as an Investigator under the guidelines of Good Clinical Practice (GCP) local regulations and the study protocol. I agree to conduct the study according to these guidelines and to appropriately direct and assist the staff under my control who will be involved in the study.

Investigator Name:	Title:
Signature:	Date:

On behalf of the Sponsor:

Name:	Title:	
Signature	Date:	

SYNOPSIS

Study Title:	Phase II, Open-Label, Single-Arm Study to Assess the Efficacy and Safety of Decapeptyl® SR (3 mg and 11.25 mg formulations) when administered by subcutaneous injection.
Study Objectives:	The purpose of this study is to evaluate the efficacy, safety and tolerability of Decapeptyl [®] SR when administered by subcutaneous (SC) injection.
	For the purpose of this study, patients will be considered to be responders if they achieve a Serum Total Testosterone Castration Level (STTCL), which is defined as a Serum Total Testosterone (STT) level of \leq 50 ng/dL.
	Primary Efficacy Study Objective
	To evaluate the efficacy of Decapeptyl SR when given by SC injection in patients with prostate cancer. This will be determined by evaluating the proportion of patients who achieve STTCL 4 months after the first injection.
	Secondary Study Objectives
	1. To evaluate the efficacy of an initial treatment with Decapeptyl SR 3 mg when given by SC injection. This will be determined by evaluating the proportion of patients who achieve STTCL 1 month after the first injection.
	2. To evaluate the efficacy of a repeat treatment with Decapeptyl SR 11.25 mg when given by SC injection. This will be determined by evaluating the proportion of patients who achieve STTCL 1 month after the second injection.
	3. To assess the changes in plasma triptorelin levels after administration of Decapeptyl SR by SC injection at all assessment time-points in comparison to Baseline.
	4. To assess changes in the levels of Serum Total Testosterone (STT) and Prostate Specific Antigen (PSA), after administration of Decapeptyl SR via the SC route at all assessment time-points in comparison to Baseline.
	Safety & Tolerability Objectives:
	1. To assess the safety of Decapeptyl SR when administered by SC injection.
	 To assess the tolerability of Decapeptyl SR when administered by SC injection.
Study Design:	This is an open-label, single-arm trial designed to assess the efficacy, safety and tolerability of Decapeptyl SR when administered by SC injection. Enrolled patients will be those who have a diagnosis of prostate cancer and for whom medical castration by means of LHRHa

is indicated. Each patient's participation in the trial will last up 5 months (including Screening period).
During the study, patients will receive one injection of Decapeptyl SR 3 mg (the 1-month sustained release formulation) and one injection of Decapeptyl SR 11.25 mg (the 3-month sustained-release formulation). The 3 mg injection will be administered at the study visit 2, on Day 0 (Baseline) and the 11.25 mg injection will be administered one month later, at visit 3. Patients will have additional follow-up visits at Month 2 and Month 4 (End of Study Visit).
All visit dates will be calculated based on calendar months in order to ensure consistency with the recommended injection schedule for Decapeptyl SR.
Written informed consent will be obtained from all patients prior to any study related procedures or assessments being performed.
All study visits will begin between 09:00 and 11:00 hours as blood samples must be collected during this time window (due to possible diurnal variations in testosterone levels)
Potential patients will be invited to attend a Screening visit (visit 1) for the study. At the Screening visit the following will be collected:
• Informed consent.
• Demographic details (date of birth, sex, ethnic origin, height, weight).
• Relevant medical history.
• Physical examination findings (including digital rectal examination (DRE) if this has not been done within 4 weeks prior to this visit).
• Vital signs (height, weight, sitting blood pressure, pulse rate).
• Blood samples (for analysis of serum total testosterone (STT), PSA, haematology and biochemistry).
• Urine sample (for dipstick urinalysis).
• Prior and concomitant medications.
Patient's eligibility of the study will be checked by reviewing the inclusion and exclusion criteria. Eligible patients will then return to the clinic within the following month for the Baseline visit.
At the Baseline visit:
• Patients' eligibility for the study will be re-checked.
• Blood samples will be collected for analysis of STT, PSA, plasma triptorelin and Liver Function Tests (LFTs) prior to receiving their injection.
 Any adverse events or changes in concomitant medications since the Screening visit will be recorded.
Patients who are still considered to be eligible for the study after completion of all Baseline assessments will then receive a SC injection
of Decapeptyl SR 3 mg . Subcutaneous injections should be

	-
	administered into the anterior abdominal wall. Details of any immediate injection site reaction(s) will be recorded.
	To minimise risk of tumour flare, all patients will start adjuvant therapy with an anti-androgen, cyproterone acetate (CPA). Each patient will take 100 mg CPA, three times a day, for 2 weeks starting on the day of the Baseline visit.
	24 hours after the injection, the site will call the patient to check whether there have been any tolerability issues following the injection. Details will be recorded in the patients CRF.
	One month after Baseline, patients will be required to attend the clinic for a follow up visit and repeat treatment (Visit 3). At this visit the following will occur:
	• Blood samples will be collected for analysis of STT, PSA, plasma triptorelin and liver function tests (LFTs).
	• Any new or altered adverse events or concomitant medications will be recorded.
	• Patients will then receive a SC injection of Decapeptyl SR 11.25 mg . Subcutaneous injections should be administered into the anterior abdominal wall. Details of any immediate injection site reaction(s) will be recorded.
	24 hours after the injection, the site will call the patient to check whether there have been any tolerability issues following the injection. Details will be recorded in the patients CRF.
	Patients will return to the clinic for a follow up assessment 2 months after the Baseline visit (visit 4). At this visit any new or altered adverse events or concomitant medications will be recorded. Blood samples will be collected (for analysis of levels of STT, PSA and plasma triptorelin).
	Four months after the Baseline visit, patients will return for an End of Study Visit (Visit 5) a physical examination will be performed and vital signs (weight, blood pressure, pulse rate) will be recorded. Blood samples will be collected (for analysis of levels of STT, PSA, plasma triptorelin, haematology and biochemistry). A dipstick urinalysis will be performed. Details of any new or altered adverse events or concomitant medications will be recorded.
	At the end of their study participation, patients will receive the standard medical care for their prostate cancer. This may involve treatment with Decapeptyl SR or any other marketed LHRHa at the discretion of the treating physician.
Study Population:	Approximately 50 patients will be enrolled in order to achieve 42 evaluable patients at the end of the study.
	Patients must satisfy the following eligibility criteria:
	Inclusion Criteria
	Patients must fulfil all of the following criteria in order to be included in the study:

1.	The patient has given written (personally signed and dated) informed consent before starting any study-related procedure, which means any assessment or evaluation that would not have formed part of their normal medical care.
2.	The patient is male and is 18 years of age or older.
3.	The patient has a histologically or cytologically confirmed diagnosis of prostate cancer and meets the following criteria:
	 Stage T3 or T4, N (any), M (any) (see Appendix 1) with a PSA >5ng/ml or
	 Biochemical relapse following radical prostatectomy or radical radiotherapy for prostate cancer
4.	Medical castration by means of LHRHa therapy is indicated for the patient.
5.	The patient has a life expectancy of at least 12 months.
6.	The patient is able and willing to comply with the requirements of the protocol.
Ex	clusion Criteria
	tients who fulfil any of the following criteria, will not be included in e study:
1.	The patient has undergone bilateral orchidectomy.
2.	The patient is either scheduled to receive, receiving, or is anticipated to require any chemotherapy for prostate cancer, or any other cancer, during the period of his participation in the study.
3.	The patient is either scheduled to receive, or anticipated to require any surgical intervention for their prostate cancer during the period of his study participation.
4.	The patient has any condition that in the opinion of the Investigator may preclude the administration of subcutaneous Decapeptyl SR injections.
5.	The patient has received treatment with any LHRHa within 1 year prior to study entry.
6.	The patient has a history of hypersensitivity to Decapeptyl SR or CPA or to any of the excipients of Decapeptyl SR or CPA.
7.	The patient has any contraindication to treatment with anti- androgens, including, but not limited to clinically significant abnormalities in liver function.
8.	The patient has been treated with oestrogens or steroid androgens within the 12 months prior to screening, or is receiving treatment with non-steroid anti-androgens at the time of the Screening visit.
9.	The patient, in the opinion of the Investigator is at risk of serious complications in the event of tumour flare (e.g. vertebral metastases threatening spinal cord compression, significant obstructive

r	
	uropathy) on initiation of Decapeptyl SR treatment, despite concomitant treatment with anti-androgens.
	10. The patient has any other condition that, in the opinion of the Investigator, might increase the risk to the patient or decrease the chance of obtaining satisfactory data needed to achieve the objective(s) of the study.
	11. The patient is likely to require treatment during the study with drugs that are not permitted by the study protocol (For a list of drugs not permitted see Appendix 2).
	12. The patient has received any investigational drug, within 30 days prior to the study or is scheduled to receive such a drug during the study.
	13. The patient has a history of, or known current, problems with alcohol abuse.
	14. The patient has any mental condition rendering him unable to understand the nature, scope and possible consequences of the study.
	15. The patient has previously been enrolled in this study.
Study Treatment:	Study Product: Decapeptyl SR (triptorelin acetate)
	Decapeptyl SR (triptorelin acetate) is a micro-particle, sustained release LHRHa that is licensed for the treatment of advanced prostate cancer in the UK. The doses/formulations to be used in this study are within the constraints of the UK product licence:
	• Decapeptyl SR 3 mg (1-Month formulation).
	• Decapeptyl SR 11.25 mg (3-Month formulation).
	These formulations are already licensed in the UK for administration by intramuscular injection. Triptorelin (Gonapeptyl 3mg) is licensed for SC and IM administration.
	The treatment regimen in this study is consistent with the recommended treatment for prostate cancer in this patient population, as documented in the Summary of Product Characteristics (SPC) for Decapeptyl SR (see Appendix 3).
	The investigational product will not be used for purposes other than as defined in this protocol. Administration of the study drug will be performed by the Investigator, or study staff to whom this task has been delegated by the Investigator.
	Concomitant medication: Cyproterone Acetate 100mg three times daily, from Baseline Visit to Day 14.
Study Evaluations:	Primary Efficacy Variables:
	The proportion of patients with STT $\leq 50 \text{ ng/dL 4}$ months after their first injection of Decapeptyl SR.
	Secondary Efficacy Variables:
	Proportion of patients with STT \leq 50 ng/dL 1 month after their first

	injection of Decapeptyl SR.
	Proportion of patients with STT \leq 50 ng/dL 1 month and 3 months after the second injection of Decapeptyl SR.
	Plasma triptorelin levels at all assessment time-points.
	STT and PSA levels at all assessment time-points.
	Safety Variables:
	1. Safety of subcutaneous route of administration will be assessed by examining the incidence of adverse events (AEs) and changes in concomitant medications at each assessment time-point.
	2. Tolerability of the subcutaneous route of injection will be assessed by observation of the injection site and by means of a phone call 24 hours after each injection. Patients will provide feedback on the following parameters.
	• Pain (severity, time of onset in relation to the injection, duration).
	• Redness (severity, time of onset in relation to the injection, duration).
	• Swelling (severity, time of onset in relation to the injection, duration).
	Severity of injection site reactions will be graded using a 4 point scale (none, mild, moderate and severe).
Statistical Methods:	The trial will test the null hypothesis (H0) that the proportion of responders (defined as a patient who achieve STTCL (≤ 50 ng/dL) 4 months after the first injection is lower or equal to 80% against the alternative hypothesis H1 that the proportion of responders is larger or equal to 95%.
	We aim to show that the percentage of patients who achieve STTCL is larger than 80%: To achieve this, a total of 42 patients are needed and the cut-off for success is 39 patients who respond to treatment. Considering the method developed by A'Hern for exact calculation in single-stage phase II designs, a sample of 42 patients with a cut-off value fixed at 39 patients allows the rejection of the null hypothesis with an alpha-risk of 2% (one sided) and an 84% power. A drop out rate of up to 10% is anticipated and to accommodate withdrawals the study sample size has been increased to 47 patients in total. The primary endpoint will be test the null hypothesis H0 that the
	The primary endpoint will be test the null hypothesis H0 that the proportion of responders is lower or equal to 80% against the alternative hypothesis H1 that the proportion of responders is larger or equal to 95%. All variables analysed will be summarized in tables, which will include the descriptive statistics, as well as inferential statistics. The exact binomial test will be used for all analyses of proportions using a significance level of 0.025. 95% confidence intervals will be presented in all cases using Stata version 9.

TABLE OF CONTENTS

1.	LIS	T OF ABBREVIATIONS		
2.	BAG	ACKGROUND INFORMATION13		
	2.1	Disease Review		
	2.2	Compound Review	14	
	2.3	Clinical Trial Rationale	15	
	2.4	Primary Objective	16	
	2.5	Secondary Objectives	16	
3.	STU	JDY DESIGN	16	
	3.1	Study Design	16	
	3.2	Study Population		
	3.3	Study Duration		
	3.4	Study Schedule		
	3.5	Study Visits		
		3.5.1 Visit 1 - Screening (within 4 weeks prior to Baseline) – For ALL		
		Patients	17	
		3.5.2 Baseline (Week 0)	18	
		3.5.3 Visit 3 (month 1)	19	
		3.5.4 Visit 4 (month 2)	19	
		3.5.5 Visit 5 (day 112:) Study Completion / Early Termination Visit	19	
4.	SEL	LECTION & WITHDRAWAL OF SUBJECTS	20	
	4.1	Patient Selection Criteria	20	
		4.1.1 Inclusion criteria	20	

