8.2 Analyses Populations Definitions

•	Screened population:	All subjects enrolled
•	Safety population:	All subjects who received at least one injection of study medication .
•	Intention-to-treat (ITT) population:	All treated subjects
•	Per protocol (PP) population:	All subjects in the ITT population for whom no major protocol violations / deviations occurred

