8.2.1 Populations Analysed

The primary analysis based on the primary efficacy endpoint(s) will be performed on the ITT population. In addition, a secondary analysis will be performed using the PP population.

All secondary analyses will be carried out using the ITT population.

The analyses of safety data will be performed based on the Safety population.

The rules for the allocation of subjects to each of the analysis populations will be defined and documented during a data review meeting held prior to database lock. During the data review meeting, based on minor or major protocol violations / deviations, subjects may be excluded from the ITT/PP populations.

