8.3 Sample Size Determination

The trial will test the null hypothesis (H0) that the proportion of responders (defined as a subject who achieve STTCL (< 50 ng/dL) 4 months after the first injection is lower or equal to 80% against the alternative hypothesis H1 that the proportion of responders is larger or equal to 95%.

Considering the method developed by A'Hern for exact calculation in single-stage phase II designs, a sample of 42 subjects with a cut-off value fixed at 39 subjects allows the rejection of the null hypothesis with an alpha-risk of 2% (one sided) and an 84% power. A drop out rate of up to 10% is anticipated and to accommodate withdrawals the study sample size has been increased to no more than 50 subjects in total.

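### The success count of 39 responders is valid only for 42 analysed patients and conflicts with the protocol's own exact test at 0.025 once the ITT set exceeds 42; the protocol does not say which rule governs

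*Protocol*

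**What the plan says.** The hypotheses are a responder proportion of at most 80% (null) against at least 95% (alternative). A responder is a patient at castrate testosterone 4 months after the first injection.

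The protocol gives two ways of deciding the primary endpoint.

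- **A count.** The Synopsis, Statistical Methods, says "a total of 42 patients are needed and the cut-off for success is 39 patients who respond to treatment". Section 8.3 repeats that "a sample of 42 subjects with a cut-off value fixed at 39 subjects allows the rejection of the null hypothesis". The stated operating characteristics are an "alpha-risk of 2% (one sided) and an 84% power".
- **A test.** The same part of the Synopsis says "The exact binomial test will be used for all analyses of proportions using a significance level of 0.025". Section 8.3.1 sets the primary test as one-sided with a 2.5% type I error.

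On who is analysed, section 8.2.1 says "The primary analysis based on the primary efficacy endpoint(s) will be performed on the ITT population", and section 8.2 defines that population as "All treated subjects". Section 8.1 defines a drop-out as a treated subject, so drop-outs belong to ITT. For up to 10% drop-out, the Synopsis raises the sample to 47 in total; section 8.3 raises it to no more than 50. The Synopsis (Study Population) plans about 50 enrolled to obtain 42 evaluable. No threshold is given for any number other than 42.

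**The concern.** A count of responders controls the false-positive risk only for the denominator it was derived from. Here the patients added to cover drop-out are treated patients. They enter the primary denominator, while the printed count stays at 39. The exact test adapts to the denominator and the count does not.

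At stake is the verdict of the trial. For a range of plausible results one rule declares the subcutaneous route successful and the other does not, so the choice could end up being made after the results are known. At the extreme, 39 of 50 is 78.0%, below the null value of 80%, yet it meets the printed count.

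**Working it through.** **Inputs.** p0 = 0.80, p1 = 0.95, n = 42, count 39, drop-out 10%, sample 47 (Synopsis) or at most 50 (section 8.3), one-sided level 0.025 (Synopsis and section 8.3.1).

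**Formula.** For n analysed and threshold r, P(X ≥ r | n, p) = Σ from k = r to n of C(n,k) p^k (1−p)^(n−k). Alpha uses p = 0.80; power uses p = 0.95.

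**Step 1: reproduce the plan.** n = 42, r = 39 gives alpha 0.0208 and power 0.8431, matching the stated 2% and 84%. Inflation: 42 / 0.90 = 46.7, rounded up to 47, matching the Synopsis. The plan's arithmetic is correct.

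**Step 2: keep 39, let n grow, and compare with the exact test.** The third column is the smallest r with P(X ≥ r | n, 0.80) ≤ 0.025.

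| n analysed | P(at least 39) at true 80% | Count needed by exact test | Its alpha | Its power at true 95% |
|---|---|---|---|---|
| 41 | – | 38 | 2.44% | 85.3% |
| 42 | 2.1% | 39 | 2.08% | 84.3% |
| 43 | 5.1% | 40 | 1.78% | 83.3% |
| 44 | 10.2% | 41 | 1.51% | 82.3% |
| 45 | 17.7% | 42 | 1.29% | 81.3% |
| 46 | 27.3% | 43 | 1.10% | 80.3% |
| 47 | 38.4% | 44 | 0.93% | 79.3% |
| 48 | 50.0% | 44 | 2.48% | 90.9% |
| 49 | 61.2% | 45 | 2.14% | 90.3% |
| 50 | 71.1% | 46 | 1.85% | 89.6% |

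The second column is also the exact p-value of observing 39 responders. At 39/47 (83.0%) it is 0.38; at 39/50 (78.0%) it is 0.71. The rules give opposite verdicts for 39 to 43 responders at n = 47 and for 39 to 45 at n = 50. At n = 41 they differ the other way: 38 responders passes the test but misses the count.

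**Step 3: allow for drop-out.** The protocol states no rule for a missing month-4 result. As an assumption, let each treated patient drop out at random with probability 0.10 and count as a non-responder. The response rate over all treated is then 0.80 × 0.90 = 0.72 under the null and 0.95 × 0.90 = 0.855 under the alternative.

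- Fixed count of 39: false-positive risk 6.0% at n = 47 and 21.8% at n = 50.
- Exact test: power 7.6% at n = 47 (needs 44) and 13.1% at n = 50 (needs 46).

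With exactly 5 drop-outs counted this way, at most 47 − 5 = 42 can respond against 44 needed, or 50 − 5 = 45 against 46 needed. The required count is out of reach. The stated 84% power therefore belongs to 42 patients with complete data.

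**The case against.** The best defence is that 39 is only a design figure. Both sections print it next to 42, the Synopsis aims for 42 evaluable patients, section 8.3.1 on significance testing contains no count, and no sentence tells anyone to apply 39 to 47 or 50. The test that is stated adapts to the number analysed and holds the error at or below 2.5%.

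Much of this stands. A reader might infer that the trial has a false-positive risk of 38% to 71%. The documents do not support that as a flat statement. It requires the count to override the stated test, and it requires 47 to 50 treated patients all with month-4 results. Those sizes are a planning range: section 8.1 defines enrolled as consented, so the planned 50 enrolled include screen failures, and section 8.2.1 allows exclusions from ITT. If 47 were treated and exactly 5 dropped out and counted as non-responders, the count of 39 would carry its design alpha of 2.1%. Nor is there an arithmetic error, since 2%, 84% and 47 all reproduce.

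Section 8.5 may also limit the damage. Recruitment closes and a monitoring committee is convened at 6 or more treatment failures, whereas 39/47 implies 8 non-responders and 39/50 implies 11. But treatment failure is not defined there and month-4 results arrive late, so this is not a dependable safeguard.

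What the defence does not remove is that the Synopsis presents 39 as the threshold for success, names a primary population not tied to 42, and gives no order of precedence between count and test.

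**Conclusion.** The concern holds as a conflict between two stated decision rules, not as a demonstrated inflation of alpha. The rules coincide at 42 and part company at every n from 43 to 50.

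The size depends on which governs. If the count governs and the true rate is 80%, the risk with complete data is 5.1% at n = 43, 38.4% at 47 and 71.1% at 50. With random 10% drop-out counted as non-response (an assumption) it is about 6% at 47 and 22% at 50. If the exact test governs, alpha is at most 2.5% throughout, but power at a true 95% and no drop-out is 79.3% at 47, below the stated 84%, and 89.6% at 50. Because the choice can reverse the primary conclusion, it should be settled before results are known.

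**What to change.** In the Synopsis and section 8.3:

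1. State that success is an exact one-sided binomial p of at most 0.025 against 80%, on the number analysed in ITT, and that 39 applies only when that number is 42.
2. Give the thresholds: 41→38, 42→39, 43→40, 44→41, 45→42, 46→43, 47→44, 48→44, 49→45, 50→46, with the same rule for any other n.
3. Disclose that power at a true 95%, before drop-out, is 79.3% for 44/47 and 89.6% for 46/50, and that 84% refers to 42 patients with complete data.
4. Reconcile 47 with the ceiling of 50, and say whether each counts enrolled or treated patients.
5. Check the chosen size against the rule for missing month-4 results, wherever that rule is set. If drop-outs count as non-responders, 5 of them make the threshold unreachable at both 47 and 50.

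Items 1 to 4 cost a few sentences and a ten-row table, with no extra patients or data. Item 5 could lead to a different sample size if drop-outs are to count as non-responders and the stated power is to be kept.
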